### ***1.2 Funding***

Diabetes Australia – Research Grant

University of Sydney DVC Research – Bridging Support Grant

Sydney Medical School Foundation - Project Grant

### ***1.3 Declaration of interests***

Nil financial or other competing interests for principal investigators to declare.

### ***1.4 Background***

Obstructive Sleep Apnoea (OSA) affects over 3.5 million Australians with approximately 25% complaining of marked sleepiness and is one of the most common health complications of obesity and central adiposity.

OSA is a disorder which is characterised by repetitive episodes of partial (hypopnea) or complete (apnoea) upper airway obstruction occurring during sleep. These episodes often result in snoring and oxyhaemoglobin desaturations that are usually terminated by brief arousals from sleep. OSA is associated with hypertension, cardiovascular disease, depression, impaired quality of life, excessive daytime sleepiness (EDS) and

impaired neurobehavioral functioning. Continuous positive airway pressure (CPAP) is considered to be the ‘gold standard’ treatment for OSA. CPAP effectively alleviates obstructive episodes during sleep and has been found to improve parameters of sleepiness, cognitive performance and functional status in patients with severe OSA; however compliance with this treatment as well as other mechanical alternatives is problematic.

Numerous cross-sectional studies show insulin resistance in OSA as measured by Homeostasis Model Assessment (HOMA) or Oral Glucose Tolerance Test (OGTT). In addition, nocturnal glucose during sleep measured with continuous glucose monitoring (CGM) has been shown to be elevated in both non-diabetic and diabetic OSA.

Randomised Controlled Trials involving treatment of OSA with CPAP versus sham CPAP or conservative treatment have been equivocal with positive effects from CPAP being more evident with high compliance, in more severe OSA and in pre-diabetes. Apart from one small study no benefit has been shown in diabetes with respect to lowering of glycosylated haemoglobin (HbA1C).

One RCT explored the combined effect of weight loss and CPAP on cardio-metabolic parameters including insulin sensitivity and blood pressure and demonstrated greater improvements with combined treatments. No studies that have looked at CGM in weight loss and OSA treatment interventions.

The only major modifiable risk factor for sleep apnoea is obesity but the efficacy of weight loss in reducing OSA in individual patients is extremely variable. As gradual weight loss is the recommended treatment approach in OSA, many patients will not immediately show an improvement in the disturbing daytime sleepiness that is often the chief clinical complaint.

The purpose of the current study is to determine in obese people with pre-diabetes, the efficacy of treating OSA with CPAP during weight loss, to achieve improvements in glucose tolerance (a measure of diabetes risk), abdominal fat loss, blood pressure and other cardio-metabolic measures at three months.

## ***1.5 Outline of the Proposed Research***

***Project Title:*** Cardio-metabolic health effects of CPAP treatment for sleep apnoea during weight loss: A Randomised Controlled Pilot Trial

***Objective:*** To determine in obese people with pre-diabetes, the efficacy of treating OSA with CPAP during weight loss, to achieve greater improvements in glucose tolerance (a measure of diabetes risk), abdominal fat loss and other cardio-metabolic measures at three months. All patients will be invited to attend a follow up visit at 12 months with reassessment of outcomes, after following a low glycaemic index (GI)/high protein diet and exercise program for nine months.

***Design:*** A three month Randomised Controlled Trial (RCT) in obese pre-diabetic patients with OSA randomised to a very low energy diet (VLED) (control) or CPAP plus VLED (intervention). Following the randomised controlled phase, patients will be re-assessed for OSA severity. Any patients with persistent OSA will commence or continue on CPAP treatment if recommended by their treating sleep physician. In addition, all patients will receive education about how to maintain a healthy weight using a low GI/high protein diet and exercise program. Optional support from a dietitian will be offered. All patients will be invited to attend a follow up visit at 12 months with reassessment of outcomes.

***Hypotheses:*** Treatment of OSA with CPAP during a VLED, compared with a VLED alone for three months, will better improve:

1. Glucose tolerance and HbA1c
2. Central Blood Pressure
3. Abdominal and total fat mass
4. Lipid profiles

***Patients:*** Female and male centrally or generally obese adults with pre-diabetes and moderate-severe OSA.

***Primary Outcome:*** Glucose tolerance, as measured by two hour blood glucose level following an oral glucose tolerance test, assessed at three months.

**Secondary Outcomes:** Abdominal and body fat, metabolic syndrome components (glucose, lipids, BP), insulin sensitivity, 24 hour blood glucose levels, 24 hour central blood pressure, health related quality of life and cost effectiveness measures.

## 2. Participants

### 2.1 Sample

**Sample size:** 30 patients randomised using a 1:1 ratio for VLED plus CPAP or VLED alone  
**Study Population:** Female and male adults with pre-diabetes and moderate-severe OSA recruited from obesity and sleep clinics and advertisements.

### 2.2 Inclusion / Exclusion Criteria

#### **Inclusion**

1. Community dwelling adults aged 18-65 years
2. Body Mass Index (BMI):  $\geq 27 \text{ kg/m}^2$  and/or waist circumference: females  $>88\text{cm}$ , males  $>102\text{cm}$  (non-European: females  $>80\text{cm}$ , males  $>90\text{cm}$ )
3. Pre-diabetes defined per World Health Organisation as any of the following recent ( $<3$  months) findings:
  - Impaired fasting glucose with BGL between 5.5 and 7.0 mmol/L
  - Impaired glucose tolerance with BGL between 7.8 and 11.0 mmol/L after a formal 75g Oral Glucose Tolerance Test (OGTT)
  - HbA1C between 6 and 6.5%
4. Moderate-severe hypoxaemic OSA with  $\text{AHI} \geq 20/\text{hr}$  and  $\text{ODI} \geq 10/\text{hr}$  prior to VLED, based on recent ( $<12$  months) polysomnography

#### **Exclusion**

1. Any known contraindications to VLED or exercise
2. Recent weight loss that in the opinion of the treating physician is clinically significant
3. Current or recent ( $<3$  months) treatment of OSA
4. Professional drivers who are sleepy
5. Recent (6 month) history of fall-asleep car crashes or near miss accidents
6. Excessive sleepiness that in the opinion of the treating physician requires immediate CPAP treatment
7. Severe medical (including renal failure) or psychiatric co-morbidity
8. Unstable medical conditions (hypertension, cardiac)
9. Recent use of illicit drugs or alcohol dependence
10. Current or recent ( $<3$  months) use of hypoglycaemic agents
11. Current or previous diagnosis of diabetes mellitus (previous gestational

---

diabetes mellitus not excluded)

12. Respiratory failure including obesity hypoventilation syndrome (OHS) (OHS as diagnosed by physician, based on standard criteria including: BMI >30kg/m^2, arterial PaCO2 >45 and evidence of prolonged periods of hypoventilation and hypoxemia during sleep)
- 

Participants will be required to inform the researcher if they are on any other medications. If this will not interfere with the study intervention and poses no greater risk to the patient, the medication will be recorded on the concomitant medication form found in Appendix C.

## ***2.3 Participant Withdrawal***

### ***Withdrawal criteria***

Participants will be informed that they have the right to withdraw from the study at any time without prejudice to their medical care, and are not obliged to state their reasons. The investigator will follow up any withdrawals.

Additionally, the investigator may withdraw a patient at any time for the following reasons:

1. If any of the study exclusion criteria are diagnosed
2. Protocol violations
3. Adverse or serious adverse events

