### ***Procedure to withdraw***

If a participant fails to return for follow up or discontinues for personal reasons, attempts will be made to determine whether the reason for not returning is not an adverse event (bearing in mind that the participant is not obliged to state his/her reasons).

Participants with clinically significant abnormalities requiring discontinuation will be followed until recovery from the abnormality, if possible.

For the reasons above, if discontinuation occurs, an early termination visit will be encouraged with an attempt to collect the primary outcome.

If the study is discontinued for safety reasons, the investigators must contact all affected participants within a reasonable time frame to inform them of the termination of their involvement in the study.

Participants discontinuing from the study may be replaced. A new randomisation number must be issued for the new participant.

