##### ***Data Analysis:***

Outcome data will be analysed using Linear Mixed Model Analysis of variance due to expected inter-patient variability and repeated measures. Patients will be random

factors. Treatment and time (0 & 3 months) will be fixed factors. The Treatment x Time interaction will be examined to see the specific difference between treatments at just the 3 month time point. Analysis will be by intention to treat and will include all participants who are randomised at 0 months including drop-ins to CPAP and participants who do not adhere to treatment.

Exploratory mixed models analyses of OSA severity accounting for CPAP compliance and weight change will also be conducted using 12 month followup data.

**Data Monitoring:** As all treatments are routinely applied in clinical care, a Data Monitoring Committee will not be appointed. Instead, all adverse events and serious adverse events will be monitored by the investigating team and discussed at regular monthly meetings. Patients who develop excessive sleepiness in the weight loss alone arm will be assessed by the study sleep physicians to determine the cause of the sleepiness and be considered on a case-by-case basis for being placed on CPAP therapy. Side effects attributable to the VLED will be managed by the dietician in consultation with the endocrinology/metabolic physician team.

There are no planned interim analyses. The final decision to terminate the trial lies with the Principal Investigators. Stopping guidelines will be based on (1) safety data and (2) ongoing trial funding. The investigators will conduct a 6 monthly review of all SAEs (pre-defined on page 22) and if after discussion the rate of SAE's is deemed unacceptable by the PI's then the study will be stopped and the HREC will be advised of the decision.

Internal procedures for monitoring trial conduct will be followed. Where available an external monitor will be engaged.

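### Withdrawal grounds that apply after randomisation conflict with the stated intention-to-treat analysis, and no rule keeps the month-3 OGTT for those withdrawn

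*Protocol*

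**What the plan says.** Protocol Section 2.3 (Withdrawal criteria) states that "the investigator may withdraw a patient at any time for the following reasons", and lists three: "If any of the study exclusion criteria are diagnosed", protocol violations, and adverse or serious adverse events. Nothing confines the first ground to findings made before randomisation. The same section adds "The investigator will follow up any withdrawals", without saying what is to be measured.

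The exclusion criteria in Section 2.2 include current or recent OSA treatment, "Excessive sleepiness that in the opinion of the treating physician requires immediate CPAP treatment", and "Current or previous diagnosis of diabetes mellitus".

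Under Procedure to withdraw, if discontinuation occurs, "an early termination visit will be encouraged with an attempt to collect the primary outcome". Discontinued participants may also be replaced.

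Section 4 (Data Analysis) states: "Analysis will be by intention to treat and will include all participants who are randomised at 0 months including drop-ins to CPAP", and goes on to include participants who do not adhere. The model has two time points, 0 and 3 months. Under Data Monitoring in the same section, a VLED-alone patient who becomes excessively sleepy is to be assessed by the sleep physicians and "be considered on a case-by-case basis for being placed on CPAP therapy". Section 1.5 defines the primary outcome as the two-hour OGTT glucose at three months.

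**The concern.** An intention-to-treat analysis needs the outcome from everyone randomised, whatever happened to their treatment. Here the conduct rules allow removal from the study for some of the very events that the analysis section says it will absorb: starting CPAP in the control arm, and not adhering. These events are related to arm. Sleepiness that calls for CPAP to be started is chiefly a control-arm event, since the other arm is already assigned CPAP, and a CPAP drop-in can occur only among controls.

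Once someone is withdrawn, the protocol names no route back to the month-3 OGTT. The month-3 value is then missing, or the only post-baseline value was taken at some other time. Section 3.2 makes the trial open label and Section 4 appoints no data monitoring committee, so the decision to withdraw is taken with the arm known. Loss that differs by arm for reasons linked to prognosis can bias the primary comparison. A later analysis plan cannot recover tests that were never sought.

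**Working it through.** **1. Expected losses.** Section 4 asks for 30 completers with about 20% dropout: 30 / (1 − 0.20) = 37.5, rounded up to 38, which reproduces the stated figure. The allowance is 38 − 30 = 8 participants, or 8/38 = 21%. At 1:1 allocation this is about 4 of 19 per arm if split evenly.

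**2. The same event under each rule.**
- *A control becomes sleepy enough to need CPAP.* Sections 2.2 and 2.3 together make this a ground for withdrawal. Section 4 has the patient assessed, possibly given CPAP, and analysed.
- *A control starts CPAP.* This meets the current-OSA-treatment criterion, so Section 2.3 allows withdrawal. Section 4 names drop-ins as included.
- *A participant in either arm does not adhere.* If this is regarded as a protocol violation, a term the protocol does not define, Section 2.3 allows withdrawal. Section 4 includes the participant.

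**3. Collection of the outcome after withdrawal.** The outcome (Section 1.5) and the model (Section 4) use month 3. Procedure to withdraw offers only an early visit that is encouraged. The general promise to follow up withdrawals names no OGTT, and the Visit 7 text in Section 3.7 does not mention those withdrawn. An early value therefore has no time point in the stated model. Its timing matters: under Dietary Component the VLED fills the first two months and a four-week transition follows, so a test before month 2 is taken on a different diet from the month-3 test.

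**4. Is there a route through glucose itself?** In Section 3.7 and Appendix A, the OGTT, HbA1c and continuous glucose monitoring fall at 0, 3 and 12 months (the 12-month OGTT only if indicated). Visits 3 to 6 are telephone calls, body measurements, vitals, food recall and lifestyle sessions. Staff have no scheduled trial glucose result between baseline and the month-3 test on which to select.

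**5. Size.** If early values were used as month-3 values, let p₁ and p₂ be the fractions affected in the two arms and d the mean difference between an early and a month-3 test. The bias in the arm difference is (p₁ − p₂) × d. With an assumed 30% and 10%, around the stated 20%, this is 0.2d. The protocol gives no d.

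If instead an equal fraction f is affected in both arms, at t months, and the effect accrues linearly (assumed), the share of the true difference retained is 1 − f(1 − t/3):
- f = 4/19, t = 0.5: 1 − 0.211 × 0.833 = 0.82
- f = 1/19, t = 2: 1 − 0.053 × 0.333 = 0.98

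Both calculations depend on a use of early values that the protocol does not state. If early values are unused, the bias depends on the unseen month-3 values of those withdrawn, and no figure follows.

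**The case against.** Four stronger readings are tempting, and the protocol does not support them.

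- *The rules remove these participants.* The wording is permissive: the investigator may withdraw, and withdrawals are to be followed up. Read literally, current OSA treatment would make the whole CPAP arm withdrawable, which cannot be intended. Section 4's specific text on drop-ins and sleepy controls may be meant to govern.
- *The early OGTT replaces the month-3 test.* No text says so. A visit is encouraged and an attempt made, and how such a value is analysed may properly sit in an analysis plan that is not shown.
- *Intention to treat is contradicted outright.* No passage deletes data, and a withdrawn participant's baseline can stay in the mixed model. The analysis is weakened by missing month-3 values, but the analysis set is not formally changed.
- *Unblinded staff can remove those with the worst glucose.* Diabetes is an exclusion criterion, but with no scheduled trial glucose test between months 0 and 3 this would need a diagnosis made outside the trial schedule. Calculations that drop the worst one or two of 15 in one arm (shifts of 0.12 and 0.23 SD) therefore describe an unlikely extreme. At 19 per arm they are 0.10 and 0.19 SD, against a standard error of √(2/15) = 0.37 SD for unadjusted means with 15 per arm.

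These points limit the size and certainty of the harm. They leave two things standing: Sections 2.2 and 2.3 do not agree with Section 4 on drop-ins, sleepiness and non-adherence, and the month-3 OGTT is nowhere retained for someone withdrawn. Both are matters of trial conduct that belong in the protocol.

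**Conclusion.** The point holds in a limited form. The withdrawal grounds are not reconciled with the analysis that Section 4 promises, and the only outcome measurement offered after discontinuation is at the wrong time for the primary endpoint. Followed as written, the rules can produce avoidable missing or mistimed month-3 data, related to arm, within an allowance of about 8 of 38. This rests on reading the first withdrawal ground as applying after randomisation, which its wording permits, and on sleepiness needing CPAP arising mainly in controls, which follows from the design.

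The protocol does not allow the bias to be sized; the figures above are illustrations under stated assumptions. Given the discretionary wording, the pilot scale and the limited scope for selection on glucose, this is something that should be fixed rather than a fatal flaw.

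**What to change.** 1. In Section 2.3, Withdrawal criteria, state that after randomisation an exclusion criterion, a protocol violation or a CPAP drop-in may lead to a study treatment being stopped but does not end follow-up. Whether treatment is stopped or started stays with the clinicians, as now.
2. In Section 2.3, Procedure to withdraw, state that unless consent is withdrawn every randomised participant is invited to the scheduled month-3 OGTT. Keep the early termination OGTT only as a fallback, recorded at its actual date and not labelled month 3.
3. Reconcile Sections 2.2, 2.3 and 4 on sleepiness so that one event does not lead both to withdrawal and to retention as a drop-in. No treatment decision need change.

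The cost is a wording amendment, with the usual ethics approval, and the recall of a few participants to a visit already in the schedule.

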### ***Discontinuation of the study***

The study may be discontinued at any time on the advice of the responsible principal investigators on the basis of new information regarding safety or efficacy. Additionally, the study may be terminated if progress is unsatisfactory or if the principal investigators fail to secure additional funding to continue the trial.

In case of premature termination or suspension of the trial, the investigator will inform the trial participants and ensure appropriate follow up and therapy. In addition, the appropriate regulatory authorities and ethics committee will be informed.

### ***Procedure to withdraw***

If a participant fails to return for follow up or discontinues for personal reasons, attempts will be made to determine whether the reason for not returning is not an adverse event (bearing in mind that the participant is not obliged to state his/her reasons).

Participants with clinically significant abnormalities requiring discontinuation will be followed until recovery from the abnormality, if possible.

For the reasons above, if discontinuation occurs, an early termination visit will be encouraged with an attempt to collect the primary outcome.

If the study is discontinued for safety reasons, the investigators must contact all affected participants within a reasonable time frame to inform them of the termination of their involvement in the study.

Participants discontinuing from the study may be replaced. A new randomisation number must be issued for the new participant.

## ***2.4 Modification of Protocol***

If any important protocol modifications are made, standard steps will be taken to gain approval from ethics for relevant documents and to re-consent affected participants with the new protocol.

## ***2.5 Recruitment Approaches***

### ***Hospitals:***

Approximately 30 participants will be entered in the pilot trial. Participants will be recruited via Woolcock, Royal Prince Alfred Hospital, University of Sydney, other affiliated sleep, endocrine and obesity physicians and advertisements.

### ***Woolcock Databases:***

The Woolcock Volunteer database hosts patient's details who have provided consent to be contacted about clinical trials. Any appropriate candidates may be contacted from this list.

***Woolcock Clinic:***

Woolcock affiliated treating physicians will be alerted to the study and asked to inform potential participants of the trial. Patients will be assured that an unwillingness to participate in the trial will in no way affect their ongoing treatment or level of care.

***Advertising:***

Advertisements will be displayed in and around waiting rooms and on websites of the institutions listed above. Advertisements may also be displayed in magazines, websites or papers and in local shops. Sleep Disorders Australia and larger general practices will also be advised of the trial to advertise the trial for potential participants.

***Media coverage:***

Media organisations will be engaged through our media liaison to outline the research study and engage public interest. Potential participants will be directed to the Woolcock Institute website where they can answer a series of eligibility questions prior to choosing whether to provide their contact details to discuss the study.

### **3. Study Design and Procedures**

#### ***3.1 Study Design***

Study Design and Duration:	A three month randomised controlled parallel group trial in obese pre-diabetic patients with OSA randomised to a VLED (control) or CPAP + VLED (intervention). The study incorporates a superiority framework. Following the randomised controlled phase, patients will commence usual clinical care of their weight maintenance and their OSA. At 12 months they will be invited to attend a follow up visit.
Outcome Measures:	Primary Outcome: Glucose tolerance as measured by an oral glucose tolerance test at three months. Secondary outcome measures of abdominal and body fat (determined from DXA scans), metabolic syndrome components (glucose, lipids, BP), health related quality of life and cost effectiveness measures will also be assessed.
Location:	Study procedures will be conducted at the Woolcock Institute of Medical Research, except the DXA scan which will be undertaken at the Charles Perkins Centre, University of Sydney.

- *The study timeline can be found in Appendix A.*

